5.2. Sample Size Determination

Although the primary objective of the trial is to demonstrate that the pooled cohort of tirzepatide (5 mg, 10 mg, and 15 mg) QW is noninferior to insulin lispro (U100) TID, relative to the primary endpoint (mean change in HbA1c from baseline to 52 weeks), sample size selection is guided by establishing noninferiority of each tirzepatide dose, tested against insulin lispro (U100), relative to the primary endpoint (mean change in HbA1c from baseline to 52 weeks). The power is assessed based on the following assumptions:

- the evaluation of noninferiority of each individual tirzepatide dose to insulin lispro (U100) will be conducted at one-sided 0.025 significance level, using a two-sample t-test
- a 0% difference in mean change in HbA1c from baseline to 52 weeks for each tirzepatide arm compared with insulin lispro (U100)
- a common standard deviation (SD) of 1.3% (accounting for increase in SD due to the inclusion of data on rescue medications and after premature treatment discontinuation and imputation of missing data)
- a noninferiority margin of 0.3%, and
- 1:1:1:3 randomization ratio (chosen to optimize power for establishing primary objective and to optimize safety comparison between pooled tirzepatide cohort versus insulin lispro).

On the basis of these assumptions, randomizing 1182 participants in a 1:1:1:3 ratio to tirzepatide 5 mg (197 participants), tirzepatide 10 mg (197 participants), tirzepatide 15 mg (197 participants) and insulin lispro (U100) (591 participants) provides 80% power to demonstrate noninferiority of each tirzepatide dose to insulin lispro (U100). Furthermore, this sample size will ensure 97% power to achieve the primary objective: establishing noninferiority of the pooled cohort of tirzepatide (5 mg, 10 mg, and 15 mg) compared to insulin lispro (U100), using a 2-sample t-test at 1-sided significance level of 0.025, provided a 0.0% difference in mean change in HbA1c from baseline to 52 weeks for the pooled cohort of tirzepatide doses compared with insulin lispro (U100), a common SD of 1.3% and noninferiority margin of 0.3%.

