6.12.1.3. Methods for Multiple Imputations

For efficacy analyses relative to the “treatment-regimen” estimand, missing HbA1c data at the 52-week visit will be imputed based on “retrieved dropouts,” defined as patients who had their HbA1c value measured at the 52-week visit in the same treatment arm who prematurely discontinued study drug. In cases where there are not enough retrieved dropouts to provide a reliable imputation model (ie, model implemented by the SAS program does not converge), an alternative multiple imputation method with reference to the baseline data (“return to baseline” approach) will be used as the primary analysis relative to the treatment-regimen estimand. If value of imputed HbA1c change from baseline is $<-6.0\%$ or $>6.0\%$, that value will be set to -6.0% or 6.0%, respectively, to avoid unrealistic imputed values. Analyses will be conducted with multiple imputations, and statistical inference over multiple imputations will be guided by the method proposed by Rubin (1987).

Imputation of missing data using retrieved dropouts may bias towards the null which favors the noninferiority outcome. A sensitivity analysis using imputation under the non-inferiority null hypothesis will also be conducted to address this limitation (Koch 2018). In this analysis, missing data will first be imputed using retrieved dropouts from each arm. Since larger negative values represent better response for HbA1c reduction, the noninferiority margin of 0.3% will be added to the imputed values in the tirzepatide arms. This approach helps to avoid bias in the direction of making tirzepatide and insulin lispro arms more similar, therefore it reduces the chance of incorrectly demonstrating noninferiority.

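### The sensitivity analysis described as imputing under the noninferiority null does so only if the retrieved dropouts in the two groups have the same mean

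*SAP*

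**What the plan says.** For the treatment-regimen estimand, SAP 6.12.1.3 imputes missing week-52 HbA1c from retrieved dropouts. These are participants in the same arm who stopped study drug early but still have a week-52 value. The SAP concedes that this may pull the arms together, which would help a noninferiority claim. In response it adds a sensitivity analysis that it describes as imputing under the noninferiority null, and it cites a published commentary for the method.

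The recipe has two steps. In this analysis "missing data will first be imputed using retrieved dropouts from each arm". After that, "the noninferiority margin of 0.3% will be added to the imputed values in the tirzepatide arms". Lispro imputations are left alone.

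The section does not link the tirzepatide imputations to lispro donors or to a common donor pool, and it neither assumes nor checks that donor means are equal. A return-to-baseline fallback is given for the primary analysis if the donor model does not converge. Whether the sensitivity analysis would use it too is not stated.

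**The concern.** The noninferiority null is a tirzepatide minus lispro difference of +0.3%. To impose it on imputed patients, the two sets of imputed values must differ by 0.3% on average. Adding 0.3% to one arm after own-arm imputation achieves that only if the donor groups were equal beforehand.

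There is a reason in the documents why they may not be equal. After stopping study drug, both groups continue glargine titration and may receive another agent (Protocol 7.1). However, lispro is listed as permitted after discontinuation in the tirzepatide arms and as not applicable in the lispro arm (Protocol 6.5, Table 10, footnote d). The documents give neither the sign nor the size of any resulting difference.

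What is at stake is the meaning of a pass or a fail. This is the only analysis the SAP sets against the bias it concedes in the retrieved-dropout method. The efficacy-estimand MMRM avoids donor imputation, but it answers a different question. A pass would naturally be read as surviving the null, which may not have been imposed. A fail could reflect a test harsher than the null.

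**Working it through.** **Inputs.** From SAP 5.2: "a common standard deviation (SD) of 1.3"%, "a noninferiority margin of 0.3"%, true difference 0, one-sided 0.025, and a "1:1:1:3 randomization ratio" (197/197/197/591). Assumed, because the documents do not give them: missing share m of 5% to 20%, equal in the two groups, and donor difference d = tirzepatide donor mean change minus lispro donor mean change. Differences are in HbA1c percentage points.

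**Step 1: reproduce the plan's power.**
- Each dose: SE = 1.3 × sqrt(1/197 + 1/591) = 0.1069. Power = Φ(0.3/0.1069 − 1.96) = 80.1%. The SAP says "insulin lispro (U100) (591 participants) provides 80% power to demonstrate noninferiority of each tirzepatide dose".
- Pooled: SE = 1.3 × sqrt(2/591) = 0.0756. Power = Φ(0.3/0.0756 − 1.96) = 97.8%, against the stated 97%.

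The inputs are therefore read correctly. The documents give no figure for the sensitivity analysis itself.

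**Step 2: what the recipe imposes.**
- Imputed contrast = (tirzepatide donor mean + 0.3) − lispro donor mean = d + 0.3.
- Contribution to the overall difference = m × (d + 0.3). Under the null it would be m × 0.3.
- Gap from the null = m × d.
- Extra strictness relative to the primary analysis = m × (d + 0.3) − m × d = 0.3 × m, whatever d is. For m = 5% to 20% this is 0.015 to 0.06.

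**Step 3: numbers at m = 10%.**

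| d | Imputed contrast | Contribution | Null contribution | Gap |
|---|---|---|---|---|
| +0.3 | +0.6 | +0.06 | +0.03 | +0.03 |
| 0 | +0.3 | +0.03 | +0.03 | 0 |
| −0.3 | 0.0 | 0.00 | +0.03 | −0.03 |
| −0.5 | −0.2 | −0.02 | +0.03 | −0.05 |
| −0.8 | −0.5 | −0.05 | +0.03 | −0.08 |

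At m = 5% every gap halves. At d = −0.5 the gap is 0.025 (m = 5%) or 0.05 (m = 10%) in size, that is 0.025/0.0756 = 0.33 or 0.05/0.0756 = 0.66 of the pooled SE.

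**Step 4: effect on the sensitivity result.** Put observed patients exactly at +0.3. The expected estimate is 0.3 + m × d, and the chance that the upper limit passes is Φ(−m × d/0.0756 − 1.96).
- At m = 10%: 0.9%, 2.5%, 5.9%, 9.7% and 18.4% for d = +0.3, 0, −0.3, −0.5 and −0.8.
- At d = −0.5: 5.2% for m = 5% and 26.2% for m = 20%.

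A four-arm simulation at m = 10% (8% donors per arm assumed, 20 imputations, Rubin's variance, no covariates, 1000 trials) gave mean estimates of 0.298, 0.270, 0.248 and 0.218 for d = 0, −0.3, −0.5 and −0.8. The formula gives 0.30, 0.27, 0.25 and 0.22. Pass rates were 1.5%, 4.5%, 7.3% and 14.9%.

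**Step 5: lispro donors plus 0.3%.** If missing tirzepatide values are drawn from lispro donors and then shifted, the imputed contrast is 0.3 for any d. In the same simulation the mean estimate stayed between 0.298 and 0.304 and the pass rate between 0.6% and 1.4%, for d from 0 to −0.8.

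**The case against.** The case for leaving the analysis alone is substantial, and much of it stands.

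- **It works in the intended direction.** A reader might infer from the algebra that the check favours tirzepatide. It does not do so relative to the analysis it tests: it is stricter at every d. Only the imputed subset can favour tirzepatide, and only if d < −0.3. No document supports a value or even a sign for d.
- **It fits the worry the SAP states.** The SAP fears imputation that makes the arms alike, which means d near 0, and there the recipe imposes the null. The SAP claims only that the approach helps against bias and lowers the chance of a wrong noninferiority finding.
- **The pass rates in Step 4 are not plain type 1 error rates.** A reader might take 5.9% to 18.4% as inflation. If donors represent the missing patients, as the primary analysis assumes, then at m = 10% and d = −0.5 the true difference is 0.9 × 0.3 + 0.1 × (−0.5) = 0.22, already inside the margin. The recipe estimates 0.9 × 0.3 + 0.1 × (−0.2) = 0.25, still conservative. These rates are errors only if the donors are unrepresentative.
- **The alternative can be weaker.** Using lispro donors discards what tirzepatide stoppers actually show. At d = +0.3 and m = 10% the present recipe contributes +0.06 and the alternative only +0.03.
- **The cited commentary cannot be consulted here.** It may define the method as an own-arm shift.
- **The fallback may close the gap.** If return to baseline were used in both arms, the imputed means would be about equal before the shift.

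None of this makes the description match the recipe when d is not 0. It limits the size of the point and rules out simply replacing the present analysis.

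**Conclusion.** The point holds in a limited form. The recipe is a 0.3% delta adjustment of own-arm imputation. It coincides with imputation under the noninferiority null only when donor means are equal, which the plan neither assumes nor checks. Its severity relative to the null therefore depends on an uncontrolled quantity and can err either way.

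The size is modest at plausible missing shares: a departure of 0.025 to 0.05 points for d = −0.5 and 5% to 10% missing, against a margin of 0.3. Both inputs are assumptions, and the formula takes the missing share as equal in the two groups.

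The documents do not support the stronger conclusions that the check is biased towards tirzepatide overall, that the trial's error rate is inflated, or that the noninferiority decision is at risk. That decision rests on the primary confidence interval (SAP 6.12.1.2), which this analysis does not enter. What is affected is how a pass or a fail on the robustness check may be described.

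**What to change.** 1. Keep the present analysis, but describe it as a 0.3% delta adjustment of own-arm retrieved-dropout imputation, equal to the noninferiority null only when donor means agree.
2. Add a second run: impute missing tirzepatide values from the lispro arm's retrieved dropouts and add 0.3%, with lispro imputed from its own donors. The imputed contrast is then +0.3% by construction.
3. Report both runs alongside the donor means by arm, and call noninferiority robust only if both hold.
4. State whether the return-to-baseline fallback applies to these runs.

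The cost is a short SAP edit and one extra imputation run, with a possibly less favourable sensitivity result. The added run should not replace the present one, because on its own it would be more lenient whenever tirzepatide donors do worse than lispro donors.

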6.12.2. Secondary Efficacy Analyses Subject to Type 1 Error Rate Control

6.12.2.1. Mean Change in HbA1c from Baseline at the 52 Week Visit

Noninferiority of individual doses of tirzepatide 5 mg, 10 mg, and 15 mg to insulin lispro (U100) will be conducted in the same manner as the primary analyses in Section 6.12.1, with individual doses of tirzepatide used in the treatment term.

Assessment of superiority of tirzepatide doses compared to insulin lispro (U100) will be conducted using the same statistical models as those used for evaluating the primary objective in Section 6.12.1. The treatment term will include tirzepatide 5 mg, 10 mg, 15 mg and insulin lispro

(U100). A linear contrast, averaging estimates from individual doses, will be used to assess the superiority of combined tirzepatide doses compared to insulin lispro (U100). Decisions will be guided by the 2-sided p-values for mean comparisons between tirzepatide doses and insulin lispro (U100) (see details in Section 6.12.3).

6.12.2.2. Mean Change in Body Weight from Baseline at the 52 Week Visit

The analysis for change in body weight from baseline (postbaseline – baseline) will be conducted in a manner similar to the primary analyses in Section 6.12.1. Baseline HbA1c category ($\leq 8.5\%$, $> 8.5\% [\leq 69, > 69 \text{ mmol/mol}]$) will be used as a fixed factor in place of baseline HbA1c as a covariate and baseline of body weight will be used as an additional covariate in the statistical model. The treatment term will include tirzepatide 5 mg, 10 mg and 15 mg and insulin lispro (U100). Least squares mean estimates of mean change in body weight from baseline will be summarized by nominal visit and by study treatment. A linear contrast, averaging estimates from individual doses, will be used to estimate the mean change in body weight from the baseline for the pooled cohort of tirzepatide doses. For the multiple imputation of missing values, if value of the imputed weight change from baseline is $<-50\text{kg}$ or $>50\text{kg}$, that value will be set to -50kg or 50kg , respectively, to avoid unrealistic values.

6.12.2.3. Analyses of Binary Outcomes

The proportion of patients achieving HbA1c values $<7.0\%$ at the 52-week visit relative to the “efficacy” estimand will be conducted utilizing data from the EAS from baseline through the 52-week visit with the aid of a logistic regression. Missing HbA1c data were imputed using all the available data in the same treatment using fully conditional specification regression method. The missing data is imputed as a continuous outcome. Statistical inference over multiple imputations will be guided by Rubin (1987)

The analysis relative to the “treatment-regimen” estimand will be conducted utilizing HbA1c data in the FAS at baseline and at the 52-week visit with the aid of a logistic regression using multiple imputation of missing HbA1c data at the 52-week visit (see Section 6.12.1.3 for details) using retrieved dropouts.

After the different missing imputation methods for the “efficacy estimand” and the “treatment-regimen” estimand, the imputed values will then be dichotomized into binary outcomes based on cutoff values. The logistic regression will include model terms of treatment, country/pooled country, and baseline metformin use (Yes/No) as fixed effects, and baseline HbA1c as a covariate. The treatment term will include tirzepatide 5 mg, 10 mg, and 15 mg and insulin lispro (U100). A linear contrast, averaging estimates from individual tirzepatide doses, will be used to estimate the proportion of patients achieving HbA1c $<7.0\%$ for the combined tirzepatide doses. Statistical inference over multiple imputations will be guided by Rubin (1987).

6.12.3. Type 1 Error Rate Control Strategy for Primary and Key Secondary Efficacy Analyses

Since they are intended for different purposes, no type 1 error rate adjustments will be made for conducting analyses relative to “efficacy” and “treatment-regimen” estimands. For analyses

within each estimand, the type 1 error control strategy for evaluation of the primary and key secondary objectives is illustrated in [Figure GPHD.6.1](#).

The primary and key secondary objective hypotheses are as follows:

- $H_{p,1}$: The pooled cohort of tirzepatide (5 mg, 10 mg, and 15 mg) QW is noninferior to insulin lispro (U100) TID, relative to the mean change in HbA1c from baseline to 52 weeks.
- $H_{p,2}$: The pooled cohort of tirzepatide (5 mg, 10 mg, and 15 mg) QW is superior to insulin lispro (U100) TID, relative to mean change in HbA1c from baseline to 52 weeks.
- $H_{p,3}$: The pooled cohort of tirzepatide (5 mg, 10 mg, and 15 mg) QW is superior to insulin lispro (U100) TID, relative to mean change in body weight from baseline to 52 weeks.
- $H_{p,4}$: The pooled cohort of tirzepatide (5 mg, 10 mg, and 15 mg) QW is superior to insulin lispro (U100) TID, relative to proportion of participants achieving target value of HbA1c <7% at 52 weeks.
- $H_{5,1}, H_{10,1}, H_{15,1}$: Each of tirzepatide arms (5 mg, 10 mg, and 15 mg) QW is noninferior to insulin lispro (U100) TID, relative to mean change in HbA1c from baseline to 52 weeks.
- $H_{5,2}, H_{10,2}, H_{15,2}$: Each of tirzepatide arms (5 mg, 10 mg, and 15 mg) QW is superior to insulin lispro (U100) TID, relative to mean change in HbA1c from baseline to 52 weeks.
- $H_{5,3}, H_{10,3}, H_{15,3}$: Each of tirzepatide arms (5 mg, 10 mg, and 15 mg) QW is superior to insulin lispro (U100) TID, relative to mean change in body weight from baseline to 52 weeks.

A graphical testing scheme (Bretz 2009) presented in [Figure GPHD.6.1](#) will be used to strongly control for type 1 error. $H_{p,1}$ will be initially tested at a two-sided 0.05 (one-sided 0.025) significance level:

[figure not shown]

Figure GPHD.6.1. Type 1 error control strategy for primary and key secondary efficacy endpoints.

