4.2. Key Secondary Objectives Subject to Strong Type 1 Error Rate Control

Together with the primary objective, the following secondary objectives are subject to strong control of the type 1 error rate (see Section 6.12.3):

- To demonstrate superiority of tirzepatide pooled cohort of 5 mg, 10 mg, and 15 mg QW versus insulin lispro (U100) TID, when added to insulin glargine (U100), with or without metformin at 52 weeks for
 - mean change in HbA1c from baseline
 - mean change in body weight from baseline, and
 - proportion of participants with HbA1c target values of <7.0% (53 mmol/mol).
- To demonstrate noninferiority of tirzepatide 5 mg, 10 mg, and/or 15 mg QW versus insulin lispro (U100) TID, when added to insulin glargine (U100), with or without metformin at 52 weeks for
 - mean change in HbA1c from baseline.
- To demonstrate superiority of tirzepatide 5 mg, 10 mg, and/or 15 mg QW versus insulin lispro (U100) TID, when added to insulin glargine (U100), with or without metformin at 52 weeks for
 - mean change in HbA1c from baseline and
 - mean change in body weight from baseline.

4.3. Other Secondary and Exploratory Efficacy Objectives Not Subject to Type 1 Error Rate Control

The following secondary efficacy objectives are not subject to strong control of the type 1 error rate:

- To demonstrate that tirzepatide (pooled cohort of 5 mg, 10 mg, and 15 mg) QW is superior to insulin lispro (U100) TID, when added to insulin glargine (U100), with or without metformin at 52 weeks for:
 - proportion of participants achieving HbA1c target $\leq 6.5\%$ (48 mmol/mol)

- mean change in fasting serum glucose (central laboratory) from baseline
- mean change in daily average 7-point self-monitored blood glucose profiles from baseline
- proportion of participants who achieved HbA1c target value of $<7.0\%$ (53 mmol/mol) without hypoglycemia (confirmed glucose <54 mg/dL [3.0 mmol/L] or report of severe hypoglycemia)
- proportion of participants who achieved weight loss of $\geq 5\%$ from baseline. and
- mean change from randomization in Short Form-36 Health Survey (SF-36v2) acute form
 - Physical Component Summary score
 - Mental Component Summary score
 - Physical Functioning domain score
 - General Health domain score
 - Vitality domain score
 - Role-Physical domain score
 - Bodily Pain domain score
 - Social Functioning domain score
 - Role-Emotional domain score
 - Mental Health domain score.

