6.12. Efficacy Analyses

Potentially for regulatory agencies, primary and key secondary efficacy assessments will be guided by the “treatment-regimen” estimand conducted using the FAS. Assessment of the primary and secondary efficacy objectives subject to type 1 error rate control (key secondary) will be conducted with multiple imputation of missing data (see Section 6.12.1.3) at 52 weeks. For publications and other purposes, the assessment of efficacy objectives will be guided by the “efficacy” estimand using the EAS without imputation of missing data.

Unless specified otherwise, the treatment term will include tirzepatide 5 mg, 10 mg, and 15 mg and insulin lispro (U100). The efficacy of the pooled tirzepatide arms compared with insulin lispro (U100) will be estimated via a linear contrast which averages the effect sizes of individual tirzepatide doses compared with insulin lispro (U100).

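### On the logistic model's own scale, the contrast planned for pooled HbA1c <7% (H_p,4) is an average log-odds; back-transformed, it is in general not the proportion of pooled patients at target

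*SAP*

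**What the plan says.** SAP 6.12.2.3 specifies the model: "The logistic regression will include model terms of treatment, country/pooled country, and baseline metformin use (Yes/No) as fixed effects", with baseline HbA1c as a covariate. The treatment factor has four levels: "The treatment term will include tirzepatide 5 mg, 10 mg, and 15 mg and insulin lispro (U100"). The pooled result is then defined by "A linear contrast, averaging estimates from individual tirzepatide doses, will be used to estimate the proportion of patients achieving HbA1c $<7.0"% for the combined doses. This applies under both estimands.

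SAP 6.12 gives the general rule that the pooled efficacy comparison is "estimated via a linear contrast which averages the effect sizes of individual tirzepatide doses compared with insulin lispro (U100"). H_p,4, listed in SAP 6.12.3, claims superiority "relative to proportion of participants achieving target value of HbA1c <7% at 52 weeks". SAP 4.2 puts the endpoint, "proportion of participants with HbA1c target values of <7.0% (53 mmol/mol"), under strong type 1 error control.

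No section states the scale of averaging, a back-transformation, standardisation over covariates, or the effect measure (odds ratio or risk difference) for H_p,4. Protocol 9.4.3.2 specifies the logistic regression and no contrast. Table GPHD.6.2 refers back to 6.12.2.3 for HbA1c ≤6.5%, HbA1c <7% without hypoglycemia, and weight loss ≥5%.

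**The concern.** Nearly the same contrast sentence appears in SAP 6.12.1.1, 6.12.1.2, 6.12.2.1 and 6.12.2.2, where the models are linear. There, the average of the dose estimates is the pooled mean. In a logistic model the estimates are log-odds conditional on country, metformin use and baseline HbA1c, so two things can go wrong:

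- Averaging logits and back-transforming gives the probability at the geometric mean of the three odds, not the mean of three proportions.
- A prediction at reference covariate values is not the average probability over the trial population.

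At stake is the headline number for a type-1-error-controlled endpoint. Two programmers could follow the text and report different pooled proportions, neither matching the share of patients at target. The three endpoints that borrow the section inherit the ambiguity.

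**Working it through.** **What the plan quantifies.** The only power figures are for HbA1c noninferiority (SAP 5.2), where the test "will be conducted at one-sided 0.025 significance level, using a two-sample t-test" and assumes "a 0% difference in mean change in HbA1c from baseline to 52 weeks for each tirzepatide arm", with SD 1.3 and margin 0.3.

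- Each dose: 0.3 / (1.3 × √(1/197 + 1/591)) = 2.805. Power = Φ(2.805 − 1.960) = 80.1%; stated 80%.
- Pooled: 0.3 / (1.3 × √(2/591)) = 3.967. Power = Φ(3.967 − 1.960) = 97.8%; stated 97%.

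Both agree and are unaffected by this point. The documents give no rate, effect size or power for H_p,4, so all rates and predictor SDs below are assumptions.

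**Step 1: logit averaging alone (no covariates).** Compare expit[(logit p₅ + logit p₁₀ + logit p₁₅)/3] with (p₅ + p₁₀ + p₁₅)/3.

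| Dose rates | Mean proportion | Back-transformed mean logit | Shift (points) |
|---|---|---|---|
| 15/25/35% | 25.0% | 24.0% | −0.96 |
| 25/35/45% | 35.0% | 34.5% | −0.46 |
| 40/50/60% | 50.0% | 50.0% | 0.00 |
| 60/70/80% | 70.0% | 70.7% | +0.68 |
| 70/80/90% | 80.0% | 81.4% | +1.41 |

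For 45/60/75%: expit[(−0.201 + 0.405 + 1.099)/3] = 60.7%, against 60.0%. The shift is zero for equal rates or rates symmetric about 50%. In this table it is negative when the rates lie below 50% and positive when they lie above. Over all rates from 10% to 95% with dose spreads up to 20 points, it ranges from −1.9 to +3.1.

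**Step 2: add the conditional-versus-marginal gap.** Let the covariate part of the linear predictor be normal with mean 0 and SD s. Solve for each arm's intercept b so that the mean of expit(b + s·Z) equals the assumed marginal rate. Then evaluate at the centre of the covariates. Differences are taken before rounding.

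*Doses 45/60/75%, lispro 30%; true pooled 60.0%, true difference 30.0 points*

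| s | Pooled, logit contrast | Lispro | Difference | Difference if the three predicted probabilities are averaged |
|---|---|---|---|---|
| 0 | 60.7 | 30.0 | 30.7 | 30.0 |
| 0.5 | 61.3 | 29.0 | 32.3 | 31.5 |
| 1.0 | 62.7 | 26.5 | 36.2 | 35.1 |
| 1.3 | 63.9 | 24.7 | 39.2 | 37.8 |

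*Doses 15/25/35%, lispro 10%; true pooled 25.0%, true difference 15.0 points*

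| s | Pooled, logit contrast | Lispro | Difference | Difference if the three predicted probabilities are averaged |
|---|---|---|---|---|
| 0 | 24.0 | 10.0 | 14.0 | 15.0 |
| 0.5 | 23.0 | 9.2 | 13.8 | 14.9 |
| 1.0 | 20.3 | 7.1 | 13.1 | 14.4 |
| 1.3 | 18.3 | 5.8 | 12.5 | 14.0 |

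In the first case most of the error comes from the conditional prediction. In the second, that error pulls both arms down and partly cancels in the difference, but the pooled proportion itself falls from 25.0% to as low as 18.3%. Some layouts are almost neutral: 25/35/45% against 15% gives 19.5 to 20.4 points (true 20.0).

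**Step 3: the test.** A simulation of 100,000 trials per setting (197/197/197/591, no covariates) applied the Wald test of the average log-odds contrast, one-sided 0.025.

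- All arms 30%: 2.4% rejection. All arms 50%: 2.7%.
- Lispro 70%, doses 60/70/80%: 4.6%. Lispro 40%, doses 30/40/50%: 1.9%.

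In the last two settings the mean dose proportion equals lispro but the mean logit does not, so the contrast tests a slightly different null.

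**The case against.** The text never says that logits are averaged. Averaging three estimated proportions is also a linear contrast and fits the words, and with 197 patients per dose equal weights match the planned pooled cohort. This stands as a point about underspecification. It does not settle the matter: the parallel wording for the linear models and the general rule in SAP 6.12 favour the model-scale reading, and averaging probabilities at reference covariates still leaves 31.5 to 37.8 points against 30 in the first case.

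An average log odds ratio is a legitimate effect size, and the SAP does not define a risk difference for H_p,4. That is correct, and the test can stay. But the sentence promises a proportion, which a log odds ratio does not supply.

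A reader might infer that the advantage over lispro will be overstated. The documents do not support that: they give no rates, the predictor SDs of 0.5 to 1.3 have no source in them, and the sign reverses at low rates. A reader might also infer that type 1 error control fails. It does not when all arms are equal; the departures shown need doses that differ yet average exactly to lispro.

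**Conclusion.** The point holds as an estimation and labelling defect. On its most natural reading, SAP 6.12.2.3 describes an average conditional log-odds and calls it a proportion; on the alternative reading it leaves the standardisation undefined. Logit averaging alone costs about 1 point or less for 20-point dose spreads at mid-range rates. The conditional-versus-marginal gap is usually larger. Together they turn 30 points into 32 to 39 in one assumed layout and 15 into 13.8 to 12.5 in another (predictor SD 0.5 to 1.3). Neither direction nor size can be fixed from the documents. The sample size, the primary analysis and the H_p,4 test under equality of all arms are not affected.

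**What to change.** In SAP 6.12.2.3, keep the logistic model and label both its pooled contrast and the H_p,4 test as an average log odds ratio against lispro. For the reported proportions, and any difference from lispro:

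1. Predict every participant's probability under each of the four arms and average over participants.
2. Average the three tirzepatide proportions on the probability scale.
3. Take any difference from lispro, with a delta-method standard error.
4. Where the endpoint is multiply imputed, do this in each imputed data set and combine by Rubin's rules.

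Apply the same standardisation to HbA1c ≤6.5%, HbA1c <7% without hypoglycemia, and weight loss ≥5%. Leave out step 4 wherever the rule in SAP 6.12.4 against explicit imputation applies.

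The cost is a few sentences of SAP text and slightly more programming. The reported difference may become smaller or larger.
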